10.12 Early Reporting to DSMB and IRBs

The conjunction of certain adverse events (AEs) and unanticipated problems will be reported promptly as they occur to the DSMB and both IRBs (see definitions for terms in section 10.5.2.2) These shall include:

- Any *serious* AE (SAE) that is also an *unanticipated* AE, and is *probably-related* or *possibly-related* to participation in the research.
- A series of *serious* AEs that are expected in some participants, but in the judgment of the investigators are occurring at a significantly higher frequency or severity than expected.
- Certain *unanticipated* AEs, regardless of severity, that might alter the IRB's analysis of the risk versus potential benefit of the research *and*, as a result, might warrant substantive changes in the research protocol such as the informed consent process and form, exclusion criteria, monitoring methods, or termination of enrollment.
- *Unanticipated problems that do not involve adverse events*, but which may have increased the risk of past or future harm to participants

In the event of any such occurrences, the Dominican investigators will document the situation in writing and notify promptly by telephone, fax, or email both the FDI IRB and the U.S. investigators, who shall notify the CDC IRB and the DSMB members, and at their discretion, the vaccine and jet injector manufacturers.

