In the Gonzalez *et al* clinical trial of Vaxigrip among children 6 months to 3 years of age, the only immediate reactions found were 9 cases of *injection site macules or papules* after the 2nd immunization (of 57, 16%), which was deemed allergic in nature. ^{Gonzalez2000} Delayed local reaction(s) occurred among 9% (5 of 57), including reddened papules of <3cm diameter, and 1 child with severe limb pain preventing voluntary movement. Thirty systemic events within 3 days after an injection were observed in 28% (16) of 57 patients. These comprised 19 events of rhinitis and cough, 5 fevers (38.5° – 38.9° C). Systemic events between 4 days and 30 after vaccination were reported after 30 1st injections and 37 2nd injections, but were deemed common childhood symptoms and not described. One patient with a history of bronchiolitis experienced 2 serious adverse events of bronchospasm occurring 25 days and 2 days after doses 1 and 2, respectively, which were deemed unrelated to Vaxigrip.

In the Saliou *et al* meta-analysis of published and unpublished Vaxigrip studies, safety results from 6 trials (including Gonzalez *et al*) were pooled into a single database. ^{Saliou2005} Among 337 subjects in the age range of 6 to 36 months, frequencies of *non-severe* AEs were 19% fever, 8.3% pain, 8.3% erythema, 2.7% induration, and 4.2% ecchymosis. *Severe* AE frequencies were 2.1% fever, 0.3% pain, 0% erythema, 0.3% induration, and 0% ecchymosis.

HIRRC/CDC Needle-free Intradermal	Page 50	File: 4785-ID-INF-Prot-Engl-2008Jun24.doc
Influenza Study - CDC-ISO-4785	of 138	2008-Jun-24

Other very rare AEs reported by the manufacturer ^{AventisPasteur2005} as a result of post marketing surveillance include:

- Blood and lymphatic system disorders (transient thrombocytopenia, lymphadenopathy)
- Immune system disorders (allergic reactions: pruritis, rash erythematous urticaria, dyspnea, angioneurotic edema, or anaphylactic shock)
- Nervous system disorders (paraesthesia, Guillain-Barre Syndrome [GBS], neuritis, neuralgia, convulsions, encephalomyelitis)
- Vascular disorders (vasculitis, with transient renal involvement in certain cases)

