10.5.2.2 Safety Variables and Monitoring

10.5.2.2.1 Definitions

Definitions and classifications for specific adverse events to be reported from this study will conform, as much as practicable, with those in draft development or finalized by the Brighton Collaboration (http://brightoncollaboration.org).

- An *adverse event* (AE) is defined as any untoward medical occurrence in a clinical investigation subject administered a pharmaceutical product, at any dose, or placebo. It does not necessarily require a causal relationship with this treatment. An AE can therefore be any unfavorable and unintended sign (including abnormal laboratory findings), symptom, or disease temporally associated with the use of a medicinal product, whether or not considered related to the medicinal product. This definition includes intercurrent illnesses or injuries, and exacerbation of pre-existing conditions.
- An *expected* AE is one previously known or anticipated as a result of (a) the interventions and interactions used in the research, (b) the collection of identifiable private information for the research; (c) an underlying disease, disorder, or condition of the human subject; and/or (d) other circumstances unrelated to the research or any underlying disease, disorder, or condition of the subject.
- An *unanticipated* AE is an unexpected occurrence or frequency of a type not previously known or commonly identified to result from (a) the

HIRRC/CDC Needle-free Intradermal	Page 80	File: 4785-ID-INF-Prot-Engl-2008Jun24.doc
Influenza Study - CDC-ISO-4785	of 138	2008-Jun-24

interventions and interactions used in the research; (b) the collection of identifiable private information under the research; (c) an underlying disease, disorder, or condition of the human subject; and/or (d) other circumstances unrelated to the research or to any underlying disease, disorder, or condition of the subject.

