10.5.2.2.5 Reporting

Any serious AE, whether or not considered study related, will be reported immediately (within 24 hours) to the U.S. PI. The individuals to be contacted at CDC for notification of a serious AE are the U.S. PI and co-investigator identified in sections 8.1.1 and 8.1.2 above, who will in turn notify the U.S. IRB and provide courtesy notification to the vaccine manufacturer.

HIRRC/CDC Needle-free Intradermal	Page 82	File: 4785-ID-INF-Prot-Engl-2008Jun24.doc
Influenza Study - CDC-ISO-4785	of 138	2008-Jun-24

Any serious or unanticipated AE must also be reported to the Dominican IRB in a timely manner. Adequate documentation must be provided to CDC showing that the IRB has been properly notified. Any medication or other therapeutic measures used to treat the event will be recorded on the appropriate case report form (CRF) page(s) in addition to the outcome of the AE.

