10.11 Data and Safety Monitoring Board

A Data and Safety Monitoring Board (DSMB) will be appointed in advance of the study (see section 8.8). Its members will certify no financial or related interests in any of the organizations conducting or cooperating with the study: CDC, HIRRC, WHO, PATH, or Bioject. Any disclosed exceptions to the certification shall be considered by the DSMB prior to material discussions so that they may be reflected in the minutes along with the DSMB's determination how to handle such exceptions. The group expertise will include the fields of vaccine science, immunization, pediatrics, public health, statistics, and clinical medical research. Statistical expertise will be provided by [name], DSMB Chair, who will be assisted, as needed, by fellow faculty and programmers of the Johns Hopkins University School of Public Health.

In advance of implementation of the study, members of the DSMB will each be provided with drafts of key study documents (protocol, consent form, case report form, diary forms, etc.) for an opportunity to review them and suggest changes on the basis of their scientific expertise and personal experience. One or more of the DSMB members will assist in preparing the allocation cards and envelopes used to randomize consecutive participant ID numbers into the three study arms. During the blinded period of the trial the DSMB will maintain in at least three separate locations the coding list to identify these allocations by study ID number.

The DSMB shall meet formally by telephone conference call at least four times: (1) prior to initiation of the study, (2) during the phase I enrollment period, (3) upon being provided with blinded clinical data from the completion of the phase I clinical aspects, and (3) upon being provided with unblinded analysis following the completion of clinical and laboratory analysis from phase II. In addition, the DSMB may meet for any requested *ad hoc* meetings as described above, or upon its own initiative for cause.

HIRRC/CDC Needle-free Intradermal	Page 104	File: 4785-ID-INF-Prot-Engl-2008Jun24.doc
Influenza Study - CDC-ISO-4785	of 138	2008-Jun-24

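### In phase II, a single related serious adverse event of a known type has no required prompt route to the DSMB, the only body that reviews by arm

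*Protocol*

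**What the plan says.** Protocol 10.12 names events that "will be reported promptly as they occur to the DSMB and both IRBs". There are four kinds:

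1. "Any *serious* AE (SAE) that is also an *unanticipated* AE, and is *probably-related* or *possibly-related* to participation in the research".
2. For events of a known kind: "A series of *serious* AEs that are expected in some participants, but in the judgment of the investigators are occurring at a significantly higher frequency"; an excess in severity counts as well.
3. Certain unanticipated AEs of any severity that might alter the risk-benefit assessment.
4. Unanticipated problems that involve no adverse event.

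The terms are defined in 10.5.2.2.1. On one side, "An *expected* AE is one previously known or anticipated as a result of (a) the interventions and interactions used in the research". On the other, "An *unanticipated* AE is an unexpected occurrence or frequency of a type not previously known or commonly identified to result from (a) the" research interventions, among other sources.

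Section 10.4.2.6 gives the manufacturer's post-marketing list. It includes "allergic reactions: pruritis, rash erythematous urticaria, dyspnea, angioneurotic edema, or anaphylactic shock" and, under nervous system disorders, Guillain-Barré syndrome and convulsions.

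The general SAE rule in 10.5.2.2.5 begins: "Any serious AE, whether or not considered study related, will be reported immediately (within 24 hours) to the U.S. PI". From there it goes to the U.S. IRB and the vaccine manufacturer, and serious or unanticipated AEs also go to the Dominican IRB. The DSMB is not among the recipients.

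Section 10.11 sets at least four formal DSMB meetings: before the study, during phase I enrolment, on completion of the phase I clinical work, and "upon being provided with unblinded analysis following the completion of clinical and laboratory analysis from phase II". It also allows ad hoc meetings on request or on the DSMB's own initiative. Section 10.9.2 suspends vaccination and calls for unblinded DSMB review once 16 of the 402 phase II vaccinees, pooled over arms, have a related SAE.

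**The concern.** The DSMB holds the coding list and is the only body set up to look at safety by arm. Investigators, assessors and parents are blinded. If one delivery method produced more related serious reactions than the others, only the DSMB could see the pattern, and only if it received the cases.

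Phase II enrols 402 of the 450 children. Section 9.6.2 states that there are no prior data on intradermal jet-injected influenza vaccine in this age group, and 12.1 relies on the stopping rules to respond quickly to any untoward risk. The events most likely to be both serious and vaccine-related are the ones already on the known list. These are the events that the first item of 10.12 leaves out of single-case reporting to the DSMB.

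The plan treats phase I differently. There the DSMB receives events by study ID at the end of the phase, and under 10.10 an excess of 3 related SAEs over control eliminates an arm. Phase II has no arm-level review until it is complete, unless a trigger fires or the DSMB meets ad hoc.

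**Working it through.** **Step 1: follow one case through the text.** Take one anaphylactic reaction in phase II, judged probably related.

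- 10.12, item 1: serious, yes; related, yes; unanticipated, no, because 10.4.2.6 lists the type as known. Not met.
- 10.12, item 2: needs a series and a judgment that frequency or severity is above expectation. Not met by one case.
- 10.12, items 3 and 4: need an unanticipated AE or a problem without an AE. Not met.
- 10.5.2.2.5: U.S. PI within 24 hours, both IRBs, manufacturer. DSMB not named.
- 10.9.2: counts the case, but triggers review only at the 16th vaccinee.
- 10.11: no scheduled phase II meeting until the phase is complete.

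A related convulsion that meets the SAE definition, or a related case of Guillain-Barré syndrome, takes the same path.

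**Step 2: reproduce the plan's figures.** The phase II trigger is 16/402 = 3.98%, stated as 4%. The phase I trigger is 3/48 = 6.25%, stated as 6%. For Guillain-Barré syndrome, 450 × 1/1,000,000 = 0.00045, as 10.4.2.7 states.

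**Step 3: outer bound of the gap.** The most vaccinees with related SAEs below the trigger is 16 − 1 = 15. That is 15/402 = 3.7% of phase II. If all were in one arm of 134, it is 15/134 = 11.2% of that arm.

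**Step 4: how often the pooled rule would react to an excess in one arm.** The protocol gives no related-SAE rate, so the rates here are assumed. Let X be binomial (134, p) for one arm and Y binomial (268, q) for the other two together. The rule fires if X + Y ≥ 16 over the whole of phase II.

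| Rate in one arm (p) | Rate in the other two (q) | Probability that the rule fires |
|---|---|---|
| 5% | 0% to 1% | 0.001 to 0.028 |
| 7.5% | 0% to 1% | 0.04 to 0.21 |
| 10% | 0% to 1% | 0.26 to 0.55 |
| 12% | 0% to 1% | 0.55 to 0.78 |

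With the same rate in all arms it fires with probability 0.008 at 2%, 0.16 at 3%, 0.54 at 4% and 0.86 at 5%.

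So with 5% in one arm (134 × 0.05 = 6.7 children expected) and at most 1% elsewhere, the pooled count stays below the trigger throughout phase II with probability of at least 1 − 0.028 = 0.972.

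**The case against.** There are real backstops. The list in 10.12 is introduced as inclusive, and its second item covers a series of expected SAEs. The protocol's own baseline for these events is very low: 10.4.2.6 calls them very rare, and Guillain-Barré syndrome has a probability of 0.00045 in the whole study. A handful of related cases could well be judged above expectation from pooled counts, without arm codes. Reaching 15 with no such judgment is an extreme case. The suspension rule counts related SAEs whether expected or not, and the DSMB may meet on its own initiative. All of this stands. It limits the size of the gap but does not supply a single case to the DSMB, and it leaves a clustering question to people who cannot see arms.

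The definition also has some give. It speaks of unexpected occurrence or frequency, and an investigator might call one anaphylaxis after intradermal jet injection unanticipated because the route is new. That is possible, but the definition of expected points the other way, so reporting would depend on who classifies the event.

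Some stronger readings are tempting but not supported:

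- *Related SAEs of known type would never reach the DSMB.* The series item, the suspension rule and ad hoc meetings all allow it.
- *The DSMB alone holds the codes.* The hospital director keeps sealed individual envelopes for emergencies (10.4.4.4, 10.6.11). The DSMB is the only body that reviews by arm.
- *10.5.2.2.5 and 10.12 contradict each other on the IRBs.* They read as two compatible tiers: all SAEs go to both IRBs, and a subset goes early.

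Section 8.8, to which 10.11 refers on the DSMB, was not in the text available to me. A reporting rule there could narrow or close the gap.

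**Conclusion.** The point holds in a narrow form. As written, one possibly or probably related SAE of a known type in phase II need not be sent promptly to the DSMB, and no scheduled meeting would bring it there before phase II is complete. The remaining routes act on a blinded judgment about a series, on 16 pooled cases, or on an ad hoc meeting that no rule supplies with such single cases.

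The figure of 15 SAEs, 11.2% of one arm, is an outer bound and not a forecast. The firing probabilities rest on assumed rates, independent children and a constant rate within each arm. They show only that the pooled rule is a weak detector of an excess in one arm. The textual gap does not depend on them. This is an inexpensive improvement to safety oversight. It does not affect the validity of the efficacy comparison.

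**What to change.** In 10.12, remove the unanticipated condition as it applies to the DSMB: every SAE judged possibly or probably related, expected or not, is sent promptly to the DSMB by study ID. Add the DSMB to the recipients in 10.5.2.2.5 for these events, and state in 10.11 that the DSMB receives them during phase II and can link them to arm. Check section 8.8 for consistency. The early-reporting tier for the IRBs can stay as it is.

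A scheduled DSMB call during phase II enrolment would be a reasonable addition but is optional.

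The cost is protocol wording and one message per related SAE. Blinding is unaffected, because the message carries only a study ID and the DSMB already holds the codes. No stopping threshold, dose or clinical rule changes.

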10.13 Changes in the Conduct of the Study or Planned Analyses

Only the sponsor (CDC, represented by the U.S. Principal and Senior Investigators) may modify the protocol. Amendments to the protocol will be made only upon consultation and agreement between the sponsor and the Department of Infectious Diseases of the HIRRC (represented by the Dominican Principal and Senior Investigators), with consultation from

HIRRC/CDC Needle-free Intradermal	Page 105	File: 4785-ID-INF-Prot-Engl-2008Jun24.doc
Influenza Study - CDC-ISO-4785	of 138	2008-Jun-24

the other cooperating institutions. The only exception is when a clinical investigator considers that a participant's safety is compromised without immediate action. In such circumstances, immediate approval of the chairman of the FDI Institutional Review Board (IRB) or ethical committee (EC) must be sought, and the investigator should inform the sponsor and the full IRBs or ECs within 5 working days after the emergency occurred.

All amendments that have an impact on participant risk or the study objectives, or require revision of the informed consent document, must be notified to the DSMB (see section 10.11) and receive approval from both the CDC and FDI IRBs or ECs prior to their implementation. The IRBs or ECs will also be routinely notified of any minor or administrative changes in the protocol. The DSMB shall also be informed and advised on major study modifications affecting scientific integrity or participant safety, such as increasing sample size.

11. Policies and Practices

11.1 Compensation, Insurance, and Indemnity

Study participant parents/guardians will receive monetary reimbursement to cover estimated transportation costs from home to the hospital for the initial recruitment trip and all followup visits related to the study. They will also receive a voucher for each visit entitling them to a snack lunch at the hospital snack bar to compensate for the extra time away from home required by the study. They may also receive a waterproof folder or carrying case for storing the participant diary, the thermometers, the circumference tape, the local reaction measurement template, and any other study materials provided to them.

The study participants will be entitled to necessary outpatient and inpatient medical care at the HIRRC similar to that available to other patients at this public institution, and at no charge for any adverse results or consequences of their participation in the study (see section 7.4).

In addition, an insurance policy will be purchased after all approvals are received from the IRB and other necessary parties to cover liability of HIRRC, CDC, and WHO for harm or damages resulting to participants from involvement in the study. The coverage will be purchased by the WHO from a reputable international insurer of clinical research worldwide, such as Biomedic-Insure (http://www.biomedic-insure.com/indexus.htm, Vannes, France), or equivalent company. Coverage shall be approximately €800,000 per protocol and a sublimit of about €160,000 per participant, equivalent as of 23 February 2006 to US\$953,754 (RD pesos 32.8m) per protocol and US\$190,737 (RD pesos 6.57m) per participant.

A summary of the above compensation, entitlement, and insurance will be mentioned in the informed consent form, but the policy amounts will NOT be disclosed, and the participant's parents will specifically be informed that coverage is for liability of the insureds to the participants, rather than direct coverage for health claims of the participants.

HIRRC/CDC Needle-free Intradermal	Page 106	File: 4785-ID-INF-Prot-Engl-2008Jun24.doc
Influenza Study - CDC-ISO-4785	of 138	2008-Jun-24

11.2 Study Material Accountability

The study investigators at the HIRRC must maintain accurate records of dates and quantities of product(s) received, to whom dispensed (subject-by-subject accounting), and accounts of any product accidentally or deliberately destroyed. The investigator must retain all unused or expired study supplies until confirmation of the accountability data by the sponsor.

11.3 Case Report Forms

Case report forms will be provided for each participant. Correction to data on CRFs may be made only by putting a line through the incorrect data and writing the correct values, allowing the original text to remain legible. Each correction must be initialed and dated by the person making the change. If corrections are made after review and signature by the HIRRC investigator, he or she must be made aware of the changes and document this awareness.

It is expected that the CRF will serve as the official medical record into which most data about the participant for this study is primarily or exclusively entered. It is the policy of this study that any other secondary data which is copied from other records into the CRF must be verifiable to the source data. This necessitates access by the sponsor, CDC, to all original recordings, laboratory reports, and participant's records. The HIRRC investigators agree to allow access to participant records and other sources for all study data, which will be maintained in confidence by CDC. The participants (or their legal representatives) must also allow access to the participant's medical records, and they will be informed of this and will be signing their agreement when giving informed consent.

11.4 Data Clarification Forms

Investigators and collaborators may have questions about the Case Report Form data after copies of the CRF data are transmitted from the study site to the sponsor. These questions will be submitted and answered by documenting them with **Data Clarification Forms** (DCFs). There are two types of DCF inquiries, *internal* and *external*:

Internal DCF: A query involving matters OTHER than safety, adverse events, and primary endpoint data, for which the resolution is self-evident. It can be answered without changing the meaning of the data (such as moving data incorrectly entered into one box on the form into another, correct box). It can be answered using logical numeric flow (for example, if the serial reporting number of an adverse event is missing, the next number in sequence can be assigned). Any of the U.S. (Sponsor) or Dominican investigators can create and answer an internal query. The U.S. Investigators will send the Dominican investigators a copy of each internal DCF completed by the Sponsor. The Dominican investigators will do the same for the U.S. Investigators on internal DCFs completed by the Dominican Investigators. The recipients will review the internal DCFs received, and if he/she disagrees, he/she will notify the other party, who will then generate a new DCF documenting the investigator's correction.

HIRRC/CDC Needle-free Intradermal	Page 107	File: 4785-ID-INF-Prot-Engl-2008Jun24.doc
Influenza Study - CDC-ISO-4785	of 138	2008-Jun-24

External DCF: A query from the U.S. Investigator (Sponsor) that requires information from the Dominican Principal Investigator, particularly on key subjects such as safety (e.g. the relationship of an adverse event to vaccination) or data on a primary endpoint (immune response, specimen identity). The Dominican investigators will provide the answer on an external DCF, sign it, and return it to the Sponsor.

